8.1.3. Immunological read-outs

Table 9 Immunological read-outs

Blood sampling timepoint		No. participants	Component
Type of contact and timepoint	Sampling timepoint		
Visit 1 (Day 1)	Pre-1 st vaccination	96	Anti-Vi antigen IgG
			Anti-O:2 IgG
			CCI
Visit 3 (Day 29)	Post-1 st vaccination	96	Anti-Vi antigen IgG
			Anti-O:2 IgG
			CCI
Visit 4 (Day 169)	Pre-2 nd vaccination	96	Anti-Vi antigen IgG
			Anti-O:2 IgG
			CCI
Visit 5 (Day 176)	Post-2 nd vaccination 1	96	Anti-Vi antigen IgG
			Anti-O:2 IgG
			CCI
Visit 6 (Day 197)	Post-2 nd vaccination 2	96	Anti-Vi antigen IgG
			Anti-O:2 IgG
			CCI

8.1.4. Cytology

Not applicable

8.1.5. Clinical safety laboratory assessments

Refer to the Section 10.2.1 for the list of clinical laboratory safety assessments required by the protocol. These assessments must be conducted according to the clinical laboratory manual and the SoA.

8.1.6. Immunological correlates of protection

No generally accepted immunological correlate of protection has been demonstrated so far for the typhoid or paratyphoid A component used in the candidate vaccine.

No antigen measurement that can assess immunological correlates of protection are planned in this study for the comparator vaccines. An antigen threshold for anti-Vi IgG of $>4.3 \mu\text{g/mL}$ (similar to the endpoint threshold used in this study) was defined as criteria of sustained protection for at least 4 years during licensing of TYPHIBEV [Kasi, 2021]. An anti-Vi IgG of $>2.0 \mu\text{g/mL}$ was estimated to be predictive of short-term protection in a previous paediatric study [Szu, 2014].

8.2. Safety assessments

The Investigator and his/her designees are responsible for detecting, documenting, and reporting events that meet the definition of an AE or SAE. This includes the assessment of COVID-19 cases as per the WHO definition [WHO, 2022]. The Investigator and designees are responsible for following up AEs that are serious, considered related to the study intervention or the study, or that caused the participant's withdrawal from the study intervention or the study.

The safety measures in this study have been planned considering the nature of the existing knowledge on the investigational vaccine components (Vi, O:2, CRM₁₉₇, Alum). The Vi component is licensed in India and WHO-prequalified; it is similar to the Bharat Biotech Typbar-TCV vaccine and the Sanofi Pasteur TYPHIM VI, both of which have been administered to millions of people worldwide with an acceptable safety profile and without particular risks. CRM₁₉₇ and Alum are well-known vaccine components with a well-characterised safety profile.

8.2.1. Pre-vaccination procedures

8.2.1.1. Collection of demographic data

Record demographic data such as month and year of birth, sex, and race in the participant's eCRF.

8.2.1.2. Medical history

Obtain the participant's medical history by interviewing the participant and/or review of the participant's medical records. Record any pre-existing conditions, signs and/or symptoms present in the last 3 years prior to the first study intervention in the eCRF.

8.2.1.3. Physical examination

A complete physical examination will be performed at screening and on each vaccination visits (Day 1 and Day 169). The physical examination will be performed by the Investigator and clinically relevant findings should be recorded in the participant source documents and in eCRF (only for enrolled participants). Physical examination includes assessment of body temperature (axillary is preferred location) and resting vital signs (systolic/diastolic blood pressure, pulse rate, and respiratory rate). On days of vaccination, body temperature and vital signs will be measured immediately prior to (maximum 60 minutes before) and 60 minutes after vaccination. Height and weight measurements will be performed during screening only. If the Investigator determines that the participant's health on the days of vaccination temporarily precludes vaccination, the visit will be rescheduled as possible by the study site.

A symptom-directed physical examination will be performed on visits where no vaccination is administered. The nature of the physical examination will be driven by any specific symptoms identified by the Investigator. The symptom-directed physical examination will not be recorded in the eCRF. However, any abnormalities detected that meet the definition of AE (refer to Section 10.3) will be recorded as such in the eCRF.

Treatment of any abnormalities observed during any physical examinations must be performed according to local medical practice outside this study or by referral to an appropriate health care provider.

8.2.1.4. Pregnancy test

Female participants of childbearing potential must take a blood pregnancy test at screening and a urine pregnancy test before the administration of any dose of study intervention. Pregnancy testing must be done even if the participant is menstruating at the time of the study visit. The study intervention may only be administered if the pregnancy test is negative.

Refer to the Section 10.4.3.1 for the information on study continuation for participants who become pregnant during the study.

8.2.1.5. Pre-vaccination body temperature

The axillary temperature of each participant needs to be measured prior to (maximum 60 minutes before) administration of any study vaccine. If the participant has fever [fever is defined as temperature $\geq 38.0^{\circ}\text{C}$ regardless of the location of measurement] on the day of vaccination, the vaccination visit will be rescheduled within the allowed interval for this visit (refer to [Table 2](#)).

8.2.1.6. Warnings and precautions to vaccination

Warnings and precautions to administration of study intervention must be checked at each visit with planned administration of study intervention.

For contraindications to the administered marketed study vaccines, refer to their SmPC and/or Prescribing Information.

8.2.2. Study holding rules and safety monitoring

Study holding rules (refer to [Table 11](#)) are introduced to ensure careful exposure to the investigational candidate vaccine and to prevent participants from being exposed to any unnecessary safety risks. The holding rules will serve as criteria to point attention to potential safety concerns and indicate requirements for additional formal committee reviews that will decide whether additional participants can be exposed to the vaccine. If the Investigator becomes aware of a holding rule threshold being met, he/she must suspend administration of the study intervention and inform IQVIA immediately. Refer to the IQVIA study contact list for contact information and [Section 8.2.2.3](#) for additional information.

Safety during the study will be monitored on an ongoing basis by the Safety Review Team (SRT), a cross-functional internal GSK committee that will evaluate safety data in a blinded manner. In addition, a GSK project-independent internal Safety Review Committee (iSRC) will be established to monitor safety at predefined timepoints and, more specifically, to recommend continuation of vaccine administration based on the unblinded safety results (refer to [Section 8.2.2.1](#)). The iSRC Chair together with the SRT will also perform blinded reviews at predefined timepoints (refer to [Section 8.2.2.1](#)), which will assess the need for full committee unblinded reviews by iSRC based on assessment of safety signals/concerns. Ad hoc safety evaluations by the iSRC may be called at any time if there are any suspected safety concerns.

The iSRC will also include an external expert (non-GSK employee); the organisation of the iSRC, the specific roles of its members, how reviews will be conducted, and how blinding will be maintained, will be outlined in the iSRC Charter.

8.2.2.1. Staggered vaccination

Participants will always be vaccinated sequentially. At Visit 1 (Day 1), sentinel participants should receive the first vaccination each 1 day apart and non-sentinel participants should receive it at least 60 minutes apart. At Visit 4 (Day 169), all participants, should receive the second vaccination at least 60 minutes apart. All participants will be closely observed for at least 60 minutes after vaccination.

The Investigator is not permitted to begin dosing study participants in Step 1b or Step 2 until the receipt of favourable written documentation of safety evaluations (iSRC/SRT). Screening procedures may continue, to facilitate the enrolment of remaining participants.

Step 1a:

A “Step 1a low dose without Alum” subgroup comprises 2 study groups (2:1 randomisation [Step 1a low dose without Alum: Step 1a control]) will receive either 2 vaccinations with the candidate low dose Vi-CRM₁₉₇+O:2-CRM₁₉₇ vaccine without Alum

or 1 vaccination with the TYPHIM VI vaccine (as control for the first vaccination) and 1 vaccination with the **CCI** [REDACTED] vaccine (as control for the second vaccination).

First, 6 sentinel participants will receive, on consecutive days, either the low dose of the Vi-CRM₁₉₇+O:2-CRM₁₉₇ or the TYPHIM VI vaccine (2:1 randomisation). Each sentinel participant will be followed up with a safety phone call approximately 1 day after vaccination. If there are any safety concerns, the sentinel participant will be asked to visit the site to assess any potential SAEs or to assess if any holding rules have been met. If no holding rules have been met nor SAEs reported by any of the sentinel participants, 12 additional participants will receive sequentially (at least 60 minutes apart) either the low dose of the Vi-CRM₁₉₇+O:2-CRM₁₉₇ or the TYPHIM VI vaccine, maintaining the 2:1 randomisation.

All available safety data (including laboratory test results) collected until 7 days after first vaccination in Step 1a will be reviewed blindly by the iSRC Chair together with the SRT (Safety evaluation #1; refer to [Table 10](#)). The iSRC Chair and SRT will decide whether an unblinded review by the full iSRC is needed, before initiating the first vaccination in Step 1b (administration of the low dose of the candidate vaccine with Alum or control vaccine to sentinel participants). A positive outcome will also allow the 18 participants in Step 1a to receive further vaccinations as per the SoA.

All available safety data (including laboratory test results) collected until 7 days after second vaccination in Step 1a will be reviewed blindly by the iSRC Chair together with the SRT (Safety evaluation #4; refer to [Table 10](#)). The iSRC Chair and SRT will decide whether an unblinded review by the full iSRC is needed, before initiating the second vaccination in Step 1b (administration of the low dose of the candidate vaccine with Alum or control vaccine to sentinel participants).

Step 1b

A “Step 1b low dose with Alum” subgroup comprises 2 study groups (2:1 randomisation [Step 1b low dose with Alum: Step 1b control]) will receive either 2 vaccinations with the low dose Vi-CRM₁₉₇+O:2-CRM₁₉₇ vaccine with Alum or 1 vaccination with the TYPHIM VI vaccine (as control for the first vaccination) and 1 vaccination with the **CCI** [REDACTED] vaccine (as control for the second vaccination).

Upon approval from the iSRC/SRT (Safety evaluation #1), 6 sentinel participants will receive on consecutive days the first vaccination with either the low dose Vi-CRM₁₉₇+O:2-CRM₁₉₇ vaccine with Alum or the TYPHIM VI vaccine (2:1 randomisation). Each sentinel participant will be followed up with a safety phone call approximately 1 day after vaccination. If there are any safety concerns, the sentinel participant will be asked to visit the site to assess any potential SAEs or if any holding rules have been met. If no holding rules have been met nor SAEs reported by any of the sentinel participants, a further 12 participants will receive sequentially (at least 60 minutes apart) either the low dose Vi-CRM₁₉₇+O:2-CRM₁₉₇ vaccine with Alum or the TYPHIM VI vaccine and **CCI** [REDACTED] vaccine, maintaining the 2:1 randomisation ratio.

All available safety data (including laboratory test results) collected until 7 days after first vaccination in Step 1b will be reviewed blindly by the iSRC Chair together with the SRT

(Safety evaluation #2; refer to [Table 10](#)). The iSRC Chair and SRT will decide whether unblinded data review by the full iSRC is needed, before initiating the first vaccination in Step 2 (administration of the full dose of the candidate vaccine with Alum, full dose of the candidate vaccine without Alum, or control vaccines to sentinel participants).

Step 2:

A “full dose with and without Alum” subgroup comprises 3 study groups (2:2:1 randomisation [Step 2 full dose without Alum: Step 2 full dose with Alum: Step 2 control]) will receive either 2 vaccinations with the full dose Vi-CRM₁₉₇+O:2-CRM₁₉₇ vaccine without Alum or the full dose Vi-CRM₁₉₇+O:2-CRM₁₉₇ vaccine with Alum or 1 vaccination with the TYPHIM VI vaccine (as control for the first vaccination) and 1 vaccination with the **CCI** [REDACTED] vaccine (as control for the second vaccination).

Upon approval from the iSRC/SRT (Safety evaluation #2), 5 sentinel participants will receive on consecutive days the first vaccination with either the full dose Vi-CRM₁₉₇+O:2-CRM₁₉₇ vaccine without Alum, the full dose Vi-CRM₁₉₇+O:2-CRM₁₉₇ vaccine with Alum, or the TYPHIM VI vaccine (2:2:1 randomisation). Each sentinel participant will be followed up with a safety phone call approximately 1 day after vaccination. If there are any safety concerns, the sentinel participant will be asked to visit the site to assess any potential SAEs or if any holding rules have been met. If no holding rules have been met nor SAEs reported by any of the sentinel participants, a further 55 participants will receive sequentially (at least 60 minutes apart) either the full dose Vi-CRM₁₉₇+O:2-CRM₁₉₇ vaccine without Alum, the full dose Vi-CRM₁₉₇+O:2-CRM₁₉₇ vaccine with Alum, or the TYPHIM VI vaccine, maintaining the 2:2:1 randomisation ratio.

All available safety data (including laboratory test results) collected until 28 days after first vaccination in Step 2 will be reviewed in an unblinded manner by the iSRC (Safety evaluation #3). The iSRC will recommend whether to proceed with second vaccination in Step 2 and allow the participants in Step 2 to complete the study as per the SoA.

Table 10 Safety evaluation schedule

Safety evaluation	Safety data reviewed	Approval to proceed to
#1: Blinded*	Up to 7 days after 1 st vaccination in Step 1a	Administration of 1 st study intervention to sentinel participants in Step 1b and subsequent administrations to participants in Step 1a
#2: Blinded*	Up to 7 days after 1 st vaccination in Step 1b	Administration of 1 st study intervention to sentinel participants in Step 2
#3: Unblinded	Up to 28 days after 1 st vaccination in Step 2	Administration of 2 nd vaccination in Step 2
#4: Blinded*	Up to 7 days after 2 nd vaccination in Step 1a	Administration of 2 nd vaccination in Step 1b

*During blinded safety evaluations, if there are any concerns that would require the evaluation of unblinded safety data, an iSRC evaluation will occur that will decide on the succeeding administration of the vaccine or to begin the next Step of the study.

Notes: All available safety data will be cumulatively reviewed at each safety evaluation (e.g., safety data after the first vaccination will be reviewed before the administration of the second vaccination). In case the safety evaluations #3 and #4 could become scheduled to occur close together, they may be combined in a single unblinded iSRC evaluation.

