8.2.2.3. Study holding rules

[Table 11](#) shows the holding rules to be implemented for this study. These holding rules have been written under the assumption that the safety data from all participants will be available. If the data from all participants are not available (e.g., in case a participant is lost to follow-up), then the holding rules will be assessed on a pro-rata basis.

Holding rules 1a-d in all steps of the study and holding rule 2c in Step 1a and 1b will be monitored by the Investigator on a continuous basis (threshold ≥ 1 , refer to [Table 11](#)). Meeting any of these holding rules will trigger a hold of study intervention administration irrespective of number of participants enrolled and/or timing of the event.

For holding rules 2a-b in all steps of the study and holding rule 2c in Step 2, the Investigator will inform IQVIA immediately if a threshold is suspected to be met, without pausing administration of the study intervention (threshold $\geq 2-6$, refer to [Table 11](#)). IQVIA will provide a report to the GVGH PP who will then confirm if the threshold has been met and advise whether to pause the study intervention administration.

If the Investigator becomes aware that a holding rule threshold has been met (either directly or via IQVIA), the following communication sequence must be followed:

- The concerned site staff must put study intervention administration on hold.
- The concerned site staff must immediately inform IQVIA CRA and Medical Monitor (contact details will be provided in a separate document) via email and phone communication who will in-turn inform the GVGH Study Responsible Project Physician.

CONFIDENTIAL

205480 (TYPH-PARATYPH A CONJ VI-CRM O2-CRM GVGH-001 (H02_01TP))
Protocol Amendment 2 Final

- All informed site staff will confirm to their local contact that action has been taken providing appropriate documentation to GVGH through the IQVIA CRA and Medical Monitor.
- GSK will further evaluate the case with the iSRC and GSK Global Safety Board and will take the decision to stop or to restart the study intervention administration. GVGH Project Physician will inform the IQVIA project lead of the decision and the rationale for the decision and all site staff will be informed by IQVIA project lead.

Table 11 Study holding rules

Holding rule	Event	Number of participants needed to pause vaccination in the study and trigger further evaluation by the iSRC		
		Step 1a	Step 1b	Step 2

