1a	Death or any life-threatening SAE regardless of causality	≥1	≥1	≥1
1b	Any non-life-threatening SAE that cannot be reasonably attributed to a cause other than vaccination as per Investigator or Sponsor assessment	≥1	≥1	≥1
1c	Any withdrawal from the study (by Investigator or participant request) following a Grade 3 AE	≥1	≥1	≥1
1d	Any solicited administration-site event or solicited systemic event leading to hospitalisation, OR Necrosis at the injection site, Each with an event onset within the 7-day post-vaccination period	≥1	≥1	≥1
2a	Any Grade 3 solicited administration-site events (lasting 48h or more as Grade 3), with an event onset within each 7-day post-vaccination period	≥3	≥3	≥6
2b	Any Grade 3 solicited systemic events (lasting 48h or more as Grade 3), with an event onset within each 7-day post-vaccination period	≥2	≥2	≥3
2c	Any Grade 3 unsolicited AE, which can be reasonably attributed to the vaccination as per Investigator or Sponsor assessment, with an event onset within each 7-day post-vaccination period OR Any Grade 3 or above abnormality* in pre-specified haematological or biochemical laboratory parameters collected at 7 days post-vaccination period	≥1**	≥1**	≥2

AE=adverse event, SAE=serious adverse event

*Refer to Section 10.9 for the grading scales to the pre-specified laboratory parameters

**The Investigator should inform IQVIA CRA and Medical Monitor immediately if an event occurs and should follow instruction as applicable to holding rules 1a-1d.

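### In Step 2, holding rule 2a needs 6 participants but the sentinel gate reads only 5, and the protocol does not clearly extend its pro-rata clause to that read

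*Protocol*

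**What the plan says.** Protocol 8.2.2.1 vaccinates 5 sentinels in Step 2, randomised 2:2:1, so 4 receive the full-dose vaccine (2 with Alum, 2 without) and 1 receives control. On spacing, "sentinel participants should receive the first vaccination each 1 day apart". On follow-up, "Each sentinel participant will be followed up with a safety phone call approximately 1 day after vaccination". The release condition is: "If no holding rules have been met nor SAEs reported by any of the sentinel participants, a further 55 participants will receive sequentially". SAP 3.1 repeats this gate and adds no threshold of its own. The Schedule of Activities (Protocol 1.3) says that the Day 2 call looks for holding-rule events as well as SAEs.

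Table 11 (Protocol 8.2.2.3) counts participants, with one column per Step. Rule 2a reads "Any Grade 3 solicited administration-site events (lasting 48h or more as Grade 3), with an event onset within each 7-day post-vaccination period", with thresholds of 3, 3 and 6 for Steps 1a, 1b and 2. Rule 2b reads "Any Grade 3 solicited systemic events (lasting 48h or more as Grade 3), with an event onset within each 7-day post-vaccination period", with thresholds of 2, 2 and 3. Rule 2c is set at 1, 1 and 2, and rules 1a to 1d at 1 throughout.

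On incomplete data, 8.2.2.3 states: "These holding rules have been written under the assumption that the safety data from all participants will be available". Where they are not available, for example "in case a participant is lost to follow-up), then the holding rules will be assessed on a pro-rata basis". The same section sends rules 2a and 2b, and rule 2c in Step 2, down a slower route labelled for thresholds of 2 to 6. The Investigator tells the CRO without pausing, and the project physician then confirms whether the threshold is met and advises on a pause.

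**The concern.** A gate that tests holding rules should be able to meet each rule it relies on. Here one of them is numerically out of reach. On the literal count, all 5 sentinels could have, say, swelling above 100 mm for two days, and rule 2a would still not be met when the next 55 are considered for dosing.

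This is the only scheduled gate between 5 and 60 participants at the full dose. Table 10 places no committee review there: the next Step 2 review, evaluation #3, uses data to 28 days after the first vaccination and releases only the second one. The full Vi dose is the licensed one, but O:2 had no human safety data before this trial (Protocol 4.3), and Step 2 raises it five-fold.

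The two possible readings of rule 2a at this read are far apart. On the literal one it can never trigger. On a pro-rata one, rounded up, a single participant triggers it. That choice should not be left until a reaction has occurred.

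**Working it through.** **1. Check the counts.** Sentinels: 6 + 6 + 5 = 17, as stated in Protocol 4.1. Step 2: 5 + 55 = 60 = 24 + 24 + 12. Total: 18 + 18 + 60 = 96, as stated. The Step 2 threshold of 6 has no stated derivation to reproduce.

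**2. Can each rule be met among the sentinels?** Compare the Table 11 count with the number of sentinels.

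| Rule | Steps 1a/1b (6 sentinels) | Step 2 (5 sentinels) |
|---|---|---|
| 1a–1d | 1: yes | 1: yes |
| 2a | 3: yes | 6: **no** |
| 2b | 2: yes | 3: yes |
| 2c | 1: yes | 2: yes |

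Only rule 2a in Step 2 fails. The probability that 5 participants yield 6 or more is 0 at any event rate. For rule 2c, only the unsolicited-event limb is likely to matter this early, because the laboratory limb uses samples taken 7 days after dosing.

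**3. What would the pro-rata clause give?** Threshold × sentinels / Step size = 6 × 5/60 = 0.5. The text has no rounding rule. Rounding up, which is an assumption here, gives 1. That lies outside the 2-to-6 label of the route to which rule 2a is assigned.

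**4. Timing against the 48-hour criterion.** Dosing is on 5 consecutive days, with a call about 1 day after each. At the fifth sentinel's call, the days since dosing are 5, 4, 3, 2 and 1. If release were decided at that call, at most 4 of 5 could have a 48-hour event, even with onset at dosing. The protocol sets no decision time, so this is conditional. The text does not say what happens when a Grade 3 reaction is still ongoing at the call.

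**5. What would a reachable count do?** The documents give no event rates, so all rates are assumptions. With n sentinels followed to 48 hours:

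- P(≥1) = 1 − (1−p)^n
- P(≥2) = 1 − (1−p)^n − n·p·(1−p)^(n−1)

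Unneeded pauses use n = 5 at a background rate p. Detection uses the n = 4 active sentinels at a high true rate.

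| Rule 2a count | Unneeded pause, p = 1% | p = 5% | Detection, p = 30% | p = 50% |
|---|---|---|---|---|
| ≥6 (literal) | 0 | 0 | 0 | 0 |
| ≥2 | 0.1% | 2.3% | 35% | 69% |
| ≥1 | 4.9% | 22.6% | 76% | 94% |

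For ≥2 of 5 at 1%: 1 − 0.9510 − 0.0480 = 0.0010. At 5%: 1 − 0.7738 − 0.2036 = 0.0226.

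**6. Cost of a count of 1 for rules 2a, 2b and 2c together in Step 2.** If the rules are independent with equal rates, the chance of an unneeded pause is 1 − 0.99^15 = 14% at 1% per rule, and 1 − 0.95^15 = 54% at 5%.

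**The case against.** The strongest reply is that the pro-rata clause already covers this. Its trigger is that data from all participants are not available, which is literally true when 5 of 60 have been dosed, and loss to follow-up is only an example. The Schedule of Activities wording about holding-rule events also suggests that single events are to be looked for at the call. This makes the pro-rata reading a fair one but does not settle it. The clause does not mention participants not yet dosed, gives no rounding rule, and produces a count that does not fit the route assigned to rule 2a. A reader might infer that the clause is excluded at the sentinel read; the documents do not say that either.

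Second, rule 2a is second-tier by design: the project physician confirms and advises, so judgement enters on either reading. That stands, and any fix should keep that route.

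Third, a reader might infer that the gate is empty, or that severe reactions would pass unexamined. The documents do not support this. Rules 1a to 1d act at one participant and cover necrosis, hospitalisation for a solicited event, and withdrawal after a Grade 3 AE. Rules 2b and 2c are reachable, and any SAE blocks release. A sentinel with a safety concern is asked to attend the site, the Safety Review Team monitors throughout, and "Ad hoc safety evaluations by the iSRC may be called at any time if there are any suspected safety concerns". Sentinel events also still count towards the Step 2 total later.

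Fourth, a reader might infer that O:2 enters Step 2 with no human experience. By then about 24 participants (12 without Alum, 12 with) should have had the low dose, with 7-day safety and laboratory data reviewed blinded at evaluations #1 and #2.

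**Conclusion.** The point holds in a narrow form and is worth correcting. At the Step 2 sentinel read, one of the seven holding rules cannot be met on its literal count, and the clause that might repair it is not clearly applied there. What is lost is a pre-specified stop for persistent severe local reactions. On the literal reading, only the remaining rules and discretionary review would then hold back the next 55 participants.

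The reachability result needs no assumption beyond Table 11 being read as written. The pro-rata value of 1 depends on rounding up. The follow-up limit of 4 in 5 depends on release at the last Day 2 call, and a site may well wait longer. The pause and detection figures rest on assumed rates and on independence between participants. Figure 1 is not visible and the iSRC charter is not among the documents, so either may say more.

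The finding does not justify lowering every second-tier count to 1. Rules 2b and 2c, and all the Step 1a/1b counts, are reachable as they stand, and step 6 of the working shows how costly that change could be.

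**What to change.** 1. In Table 11, add a Step 2 sentinel-read count for rule 2a that 5 participants can reach, for example 2 or more of 5. This fits the existing inform-and-confirm route. Because that route does not itself pause dosing, state that the other 55 are not dosed until the project physician has settled the question. Leave rules 2b and 2c and the Step 1a/1b counts as they are.
2. In 8.2.2.1, state that a Grade 3 solicited reaction still ongoing at a sentinel's Day 2 call is followed to 48 hours before the gate is judged.

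The choice between 1 and 2 belongs to the sponsor's safety team: a count of 1 detects more but pauses more often, as the table in the working shows.

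The cost is one table entry and two sentences, with no added participants or scheduled visits. The wait arises only if such a reaction is ongoing: about 48 − 24 = 24 hours after the call if it began at dosing, and at most about 48 hours if it began just before the call.

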8.2.2.2. Outcome of safety evaluation

- If no safety concern is observed during the blinded or unblinded data review, the favourable outcome of the safety evaluations will be documented and provided in writing, authorising the Investigator to start vaccination of participants with the subsequent dose as well as enrolment and vaccination of the remaining participants of the next step of the study.
- In case the Investigator becomes aware of one or more holding rules (refer to Section 8.2.2.3), he/she should immediately inform IQVIA of the event (refer to the IQVIA study contact list for contact information).
- If a safety issue is observed during the unblinded data review or if any of the holding rules (e.g. 2a or 2b; Refer to [Table 11](#)) is met, the iSRC Chair (or his/her representative) is responsible for the urgent communication to the GVGH PP, including any rationale for a decision to put the vaccination on hold or not. The GVGH PP will be accountable for notifying all investigators (through IQVIA) of the decision whether to suspend, modify, or continue the conduct of the study on all groups or on selected groups.
- If a safety issue is observed during the blinded data review or a holding rule threshold is met (not known in which study group events occurred), an ad hoc iSRC safety evaluation meeting will be called.

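### Step 2's full-dose second vaccination is formally conditional only on evaluation #3: #4 does not bind it, and no Table 10 row names Step 1b second-dose data

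*Protocol*

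**What the plan says.** Protocol 8.2.2.1 and Table 10 schedule four evaluations.

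- **#1** (blinded): Step 1a first-dose data to 7 days. It releases Step 1b first doses and further Step 1a doses.
- **#2** (blinded): Step 1b first-dose data to 7 days. It releases Step 2 first doses.
- **#3** (unblinded): safety data "collected until 28 days after first vaccination in Step 2 will be reviewed in an unblinded manner by the iSRC (Safety evaluation #3"). The internal Safety Review Committee (iSRC) then recommends whether Step 2 goes on to its second vaccination.
- **#4** (blinded): data "collected until 7 days after second vaccination in Step 1a will be reviewed blindly by the iSRC Chair together with the SRT" (SRT, the Safety Review Team). It releases second doses in Step 1b.

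The notes to Table 10 make every evaluation cumulative over whatever data are available. Their example is that "safety data after the first vaccination will be reviewed before the administration of the second vaccination". If #3 and #4 fall close together, "they may be combined in a single unblinded iSRC evaluation".

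Other controls apply throughout. If a blinded evaluation raises a concern, "an iSRC evaluation will occur that will decide on the succeeding administration of the vaccine", and under 8.2.2.2 "an ad hoc iSRC safety evaluation meeting will be called". Section 8.2.2 adds ongoing blinded SRT monitoring and allows an iSRC review on suspicion alone. The holding rules in Table 11 act across the study, as its column heading shows: "Number of participants needed to pause vaccination in the study and trigger further evaluation by the iSRC".

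**The concern.** The protocol requires second-dose data from Step 1a to be reviewed before Step 1b receives its second dose. It does not carry that requirement over to Step 2, where the second dose has five times the antigen (25 µg of each component against 5 µg) and goes to 48 candidate recipients instead of 12. The protocol gives no reason for the difference. Section 4.3 says that the O:2 component has no human safety data.

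Two things follow from the text. An unfavourable or late #4 does not by itself hold Step 2. And Step 1b, the only group to receive a second adjuvanted dose before Step 2 does, has no scheduled review in which its second-dose data are named.

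**Working it through.** The plan gives no figure on this point, so the check is on timing and on the sensitivity of the holding rules.

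**Inputs from the protocol.** Sentinels are dosed on consecutive days (6, 6 and 5 in Steps 1a, 1b and 2), followed by 12, 12 and 55 others. Each next step waits for 7-day data and a review. The second dose is planned at 168 days (158–178 allowed), and Visit 5 follows 7 days later (7–10 allowed).

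**Assumptions.** Each review takes 7 days. Non-sentinels are dosed at p per week, the same in every step; p is not stated, so 42 to 3 is used. T2 is the day of the first Step 2 first vaccination, and e = 12 × 7/p, rounded up to whole days.

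**Formulas at planned intervals.**

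- #3 data cut: T2 + 4 + (55 × 7/p, rounded up) + 28.
- First Step 1b dose: T2 − (7 + 7) − e − 5 = T2 − 19 − e.
- First Step 1b 7-day second-dose data: T2 − 19 − e + 168 + 7 = T2 + 156 − e.
- Last Step 1b 7-day second-dose data: T2 − 14 + 175 = T2 + 161, at every pace.
- #4 release: Step 1b starts 14 days after the last Step 1a first dose, so T2 − 19 − e − 14 + 175 + 7 = T2 + 149 − e.

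| p per week | e | #3 cut | First Step 1b second-dose data | Step 1b participants in #3 | #4 release |
|---|---|---|---|---|---|
| 42 | 2 | T2+42 | T2+154 | 0 of 18 | T2+147 |
| 7 | 12 | T2+87 | T2+144 | 0 of 18 | T2+137 |
| 4 | 21 | T2+129 | T2+135 | 0 of 18 | T2+128 |
| 3.5 | 24 | T2+142 | T2+132 | 8 of 18 | T2+125 |
| 3 | 28 | T2+161 | T2+128 | 18 of 18 | T2+121 |

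At 3.5 per week the six sentinels fall at T2+132 to T2+137 and the next two participants at T2+139 and T2+141, giving 8 by T2+142.

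The first planned Step 2 second dose is at T2+168. By then #4 has cleared and all 18 Step 1b participants have 7-day second-dose data, at every pace shown. So the data exist when Step 2 is boosted, but at 4 per week or faster they do not exist when #3 is cut. Merging #3 with #4 cannot bring them in, because #4 is what releases Step 1b second dosing.

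**Holding rules after Step 1b second doses.** Rule 2a needs 3 participants with a qualifying Grade 3 administration-site event; rule 2b needs 2 with a qualifying systemic event. With X binomial on 12 candidate recipients (the same formula reproduces Table 14: 1 − 0.85^12 = 85.8%):

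- Rule 2a not reached, P(X ≤ 2): 89%, 56%, 25% at assumed true rates of 10%, 20%, 30%. Adding the 6 controls at an assumed 5% gives 82%, 48%, 21%.
- Rule 2b not reached, P(X ≤ 1): 88%, 66%, 27% at 5%, 10%, 20%. With controls: 77%, 55%, 22%.

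When a 2a or 2b threshold is suspected, "the Investigator will inform IQVIA immediately if a threshold is suspected to be met, without pausing administration of the study intervention"; the sponsor's project physician then confirms it and advises on a pause.

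**The case against.** The strongest case is that existing coverage is good and the missing evidence is modest.

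- One Step 1b event under rules 1a–1d or 2c pauses vaccination, SRT monitoring is continuous, and the iSRC can meet on suspicion. A concern at #4 can lead to suspension of all groups. This stands, and it limits the gap.
- #3 is an unblinded 28-day review at the actual dose and formulations. Step 1b recipients get 0.1 mL from the 0.5 mL vial, one-fifth of the antigen, and a blinded review would mix in 6 controls. This also stands. But #3 need contain no second-dose data, and the protocol treats second-dose data as worth a separate look, since #4 exists.
- The holding-rule probabilities rest on assumed rates and count one dose only. If a participant counts for an event after either dose, with independent doses, non-trigger at 10% and 20% per dose falls to 59% and 14% for rule 2a, and to 30% and 4% for rule 2b. The text does not settle how to count.
- The iSRC Charter is a separate document and Figure 1 is not shown; either might add a review.

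A reader might go further and infer that no formal second-dose review precedes Step 2 boosting, that no scheduled evaluation could ever include Step 1b second-dose data, or that these data go unmonitored. The documents support none of these. #4 clears before T2+168 in every scenario above; it is simply not binding on Step 2. The cumulative note would bring all 18 Step 1b participants into #3 at 3 per week. And the holding rules apply after each vaccination.

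**Conclusion.** The point holds in a limited form. As written, Step 2's second vaccination depends formally on #3 alone, and #3's named content is Step 2 first-dose data. #4 normally comes first but binds Step 1b only. Unless Step 2 enrols slowly (about 3.5 per week or less with 7-day reviews), the cumulative note will not bring Step 1b second-dose data into #3.

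What is left uncovered is a required look at Step 1b second-dose patterns below the holding-rule thresholds, from 12 adjuvanted low-dose recipients, before full-dose adjuvanted boosting of 24. The missing condition on #4 affects all 48 full-dose candidate participants.

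The reading of Table 10 needs no assumption. The timing rests on planned intervals and on the assumed pace and review length. This is a cheap improvement to consider, not evidence that the design is unsafe.

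**What to change.** Amend Table 10 and 8.2.2.1 in two ways.

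**(a)** Make a favourable #4 a condition for Step 2's second vaccination as well as Step 1b's. At planned intervals this costs no time (T2+121 to T2+147). If the last Step 1a participant is boosted at day 178 with Visit 5 at day 10, #4 moves 10 + 3 = 13 days later, to T2+134 to T2+160, still before T2+168.

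**(b)** Before the first Step 2 second vaccination, add a blinded review by the iSRC Chair and SRT of all Step 1b second-dose safety data available at a cut shortly before that date. State a minimum content, for example 7-day data from the six Step 1b sentinels, and escalate to the unblinded iSRC on concern. Later Step 1b data stay under SRT monitoring and the holding rules.

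A minimum content is better than a fixed calendar cut. A cut at T2+161 holds 18 of 18 only if visits run to plan and earlier reviews took at least 7 days. It holds 2–15 of 18 if those reviews took 1 day, and 0–12 of 18 if every Step 1b booster is at day 178 with Visit 5 at day 10.

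The cost is one table row, one paragraph and one more review by existing bodies. At planned intervals the last sentinel reaches 7 days at T2 + 161 − e, so a 7-day review releases between T2+140 (3 per week) and T2+166 (42 per week). If the sponsor waits for all of Step 1b, release is at T2+168. The 7 (3 per week) to 35 (42 per week) of 60 Step 2 participants first dosed within 10 days of T2 then lose up to 10 days of their 158–178 day window. If the sentinels run 13 days late at 42 per week, release would be T2+179, one day past the first Step 2 participant's window. Their boosters should therefore be booked on time, or a shorter review agreed.

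If the sponsor prefers #3 alone, the protocol should say why Step 2 needs no required second-dose review when Step 1b does.
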